#### Artemether/lumefantrine

No particular risk associated with an over dosage of arthemeter/lumefantrine has been identified to-date by Novartis. In case of accidental over-dosage, routine supportive treatment including maintenance of a clear airway and adequate fluid intake should be provided.

## 7.12. Occupational Safety

Investigational product is not expected to pose significant occupational safety risk to site staff under normal conditions of use and administration. A Material Safety Data Sheet (MSDS)/equivalent document describing occupational hazards and recommended handling precautions either will be provided to the investigator, where this is required by local laws, or is available upon request from GSK.

#### CONFIDENTIAL

However, precautions are to be taken to avoid direct skin contact, eye contact, and generating aerosols or mists. In the case of unintentional occupational exposure notify the monitor.

Precaution will be taken to avoid direct contact with the investigational product. A Material Safety Data Sheet (MSDS) describing occupational hazards and recommended handling precautions will be provided to the investigator.

## 8. CONCOMITANT MEDICATIONS AND NON-DRUG THERAPIES

#### 8.1. **Permitted Medications**

All subjects can be given paracetamol during the study, at the discretion of the treating physician. Allowable antibiotics are penicillin, cephalosporins and aminoglycosides.

All concomitant medications taken during the study will be recorded in the eCRF. The minimum requirement is that drug name and the dates of administration are to be recorded.

#### 8.2. Prohibited Medications

Drugs from the WHO list of essential drugs known to induce haemolysis or haemolytic anaemia (see Study Reference Manual for details). Any antimalarial, or antibiotic with antimalarial activity (erythromycin and other macrolides, co-trimoxazole and other sulphonamides, any tetracycline (including doxycycline, and quinolones.

**Chloroquine:** Prior treatment with chloroquine will not be considered an exclusion criterion, however, the intercurrent use of chloroquine during the study period will be a protocol violation and cause exclusion from the per-protocol population.

## 8.3. Non-Drug Therapies

The use of herbal remedies during the course of the study should be avoided and subjects should be encouraged to return to the study clinic for treatment if they are feeling unwell in the first instance. However, if any herbal remedies are taken during the study this should be captured in the eCRF, under concomitant medication.

# 9. SUBJECT COMPLETION AND WITHDRAWAL

## 9.1. Subject Completion

A subject will be considered to have completed the study if they have received the full course of study medication and have attended all efficacy visits.

#### 9.2. Subject Withdrawal

A withdrawn subject is any subject who enters the study (i.e. gives informed consent), and is randomised to treatment, but does not complete the study (whether or not the subject received study medication).

#### 9.2.1. Subject Withdrawal from Study

A subject may be withdrawn from the study any of the following reasons:

- Adverse Event
- Lost to follow-up
- Protocol violation
- Withdrawal of consent by a subject

If a subject is withdrawn from the study the following assessments should be conducted: clinical assessment, measure temperature, take haematology and clinical chemistry samples and prepare a microscope slide, plus filter paper for *P.f.* PCR any day on or after day 7. Where possible, female subjects of child-bearing potential should be asked to take a urine pregnancy test on early withdrawal from the study.

The reason for withdrawal will be recorded in the Study Conclusion form of the eCRF.

Subjects who are withdrawn will not be replaced. The sample size has been adjusted for to allow for a generous withdrawal rate and loss-to-follow-up to 28 days, see Section 11.2.1.

#### 9.2.2. Subject Withdrawal from Investigational Product

Subjects who withdraw from the study prior to completing the full course of study medication will be given an appropriate rescue medication. The reason for withdrawal from medication will be recorded in the Investigational Product Discontinuation form of the eCRF.

Subjects withdrawing from investigational product should remain in the study for safety assessment through to day 42.

## 9.3. Treatment After the End of the Study

At the end of the study on the 42-day follow-up visit, if the subject is diagnosed with malaria, they will receive an appropriate rescue mediation, and be followed-up until resolution of that infection.

## 10. ADVERSE EVENTS (AE) AND SERIOUS ADVERSE EVENTS (SAE)

The investigator is responsible for the detection and documentation of events meeting the criteria and definition of an AE or SAE, as provided in this protocol. During the study when there is a safety evaluation, the investigator or site staff will be responsible for detecting, documenting and reporting AEs and SAEs, as detailed in both this section of the protocol and in the AE/SAE section of the SRM.

## 10.1. Definition of an AE

Any untoward medical occurrence in a patient or clinical investigation subject, temporally associated with the use of a medicinal product, whether or not considered related to the medicinal product.

Note: An AE can therefore be any unfavorable and unintended sign (including an abnormal laboratory finding), symptom, or disease (new or exacerbated) temporally associated with the use of a medicinal product. For marketed medicinal products, this also includes failure to produce expected benefits (i.e. lack of efficacy), abuse or misuse.

## 10.2. Definition of a SAE

A serious adverse event is any untoward medical occurrence that, at any dose:

- a. Results in death.
- b. Is life-threatening.

NOTE: The term 'life-threatening' in the definition of 'serious' refers to an event in which the subject was at risk of death at the time of the event. It does not refer to an event, which hypothetically might have caused death, if it were more severe.

c. Requires hospitalization or prolongation of existing hospitalization.

NOTE: In general, hospitalization signifies that the subject has been detained (usually involving at least an overnight stay) at the hospital or emergency ward for observation and/or treatment that would not have been appropriate in the physician's office or out-patient setting. Complications that occur during hospitalization are AEs. If a complication prolongs hospitalization or fulfils any other serious criteria, the event is serious. When in doubt as to whether "hospitalization" occurred or was necessary, the AE should be considered serious.

Hospitalization for elective treatment of a pre-existing condition that did not worsen from baseline is not considered an AE.

d. Results in disability/incapacity, or

NOTE: The term disability means a substantial disruption of a person's ability to conduct normal life functions. This definition is not intended to include experiences of relatively minor medical significance such as uncomplicated headache, nausea, vomiting, diarrhea, influenza, and accidental trauma (e.g. sprained ankle) which may

interfere or prevent everyday life functions but do not constitute a substantial disruption.

- e. Is a congenital anomaly/birth defect.
- f. Medical or scientific judgement should be exercised in deciding whether reporting is appropriate in other situations, such as important medical events that may not be immediately life-threatening or result in death or hospitalization but may jeopardize the subject or may require medical or surgical intervention to prevent one of the other outcomes listed in the above definition. These should also be considered serious. Examples of such events are invasive or malignant cancers, intensive treatment in an emergency room or at home for allergic bronchospasm, blood dyscrasias or convulsions that do not result in hospitalization, or development of drug dependency or drug abuse.

Additionally, the following protocol specific events will be reported as SAEs:

- g. Haemoglobin values: a drop of  $\geq 40\%$  of baseline haemoglobin and / or all blood transfusions, and/or all haemoglobin values of < 5g/dL
- h. Methaemoglobin values: all values of  $\geq 20\%$ , and /or values of  $\geq 10\%$  but <20% with associated clinical symptoms of methaemoglobinaemia.

# 10.2.1. Clinical Laboratory Abnormalities and Other Abnormal Assessments as AEs and SAEs

Abnormal laboratory findings (e.g., clinical chemistry, hematology, urinalysis) or other abnormal assessments (e.g., vital signs) that are judged by the investigator as **clinically significant** will be recorded as AEs or SAEs if they meet the definition of an AE or SAE. Clinically significant abnormal laboratory findings or other abnormal assessments that are detected during the study or are present at baseline and significantly worsen following the start of the study will be reported as AEs or SAEs. However, clinically significant abnormal laboratory findings or other abnormal assessments that are associated with the disease being studied, unless judged by the investigator as more severe than expected for the subject's condition, or that are present or detected at the start of the study and do not worsen, will **not** be reported as AEs or SAEs.

The investigator will exercise his or her medical and scientific judgment in deciding whether an abnormal laboratory finding or other abnormal assessment is clinically significant.

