#### 11.3.5.8.2. Adverse Events

Adverse Event (AE) reporting will be performed using the MedDRA (Medical Dictionaries for Regulatory Activities) coding system. Each AE coded using the MedDRA system can be associated with more than one system organ class (SOC). However, for reporting purposes, an AE will be associated with the primary system organ class only.

Counting of adverse events will be based on the number of subjects – not the number of AEs. For example, if a subject reports the same AE on three occasions within a time interval, that AE will only be counted once. Subjects reporting more than one AE in a system organ class will only be counted once in the system organ class total.

All treatment-emergent AE's (i.e. with onset time on or after that of first dose), will be listed and a summary table will be prepared showing the incidence of all recorded AEs by treatment group. However, all other AE tabulations will be produced excluding occurrences of PCR-confirmed P. fulciparum recrudescence. Such events will be classified as treatment failures for the purposes of efficacy analyses but will not be considered AEs for the purposes of comparing the AE profiles between the two treatment groups. Occurrences of new malarial infection, as confirmed by PCR will remain as adverse events and will be reported in all the AE outputs. The following summary tables will be produced for all AEs except those confirmed as recrudescences:

AE's by preferred term and SOC, AE's in descending order of frequency, AE's by maximum severity (mild, moderate or severe).

AE's considered by the investigator to have a reasonable possibility of being related to treatment ('drug-related' AEs) will be summarised by preferred term and SOC.

AE's leading to premature withdrawal from treatment will be summarised by preferred term and SOC.

AE's leading to premature withdrawal from study will be summarised by preferred term and SOC.

AE's that are considered to be haematologically-related will be identified for reporting by clinical review of blinded AE data. Haematological AE's will be summarised by preferred term and SOC.

Serious adverse events will be summarised by preferred term and SOC.

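### Section 10.2.1 has no exception for the mandatory haemoglobin SAEs of Section 10.2(g), so read literally the two sections give opposite reporting instructions

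*Protocol*

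**What the plan says.** Protocol Section 10.2 gives the usual SAE criteria (a to f) and then adds study-specific ones: "Additionally, the following protocol specific events will be reported as SAEs". Item g covers a fall of 40% or more "of baseline haemoglobin and / or all blood transfusions", and it also captures "all blood transfusions, and/or all haemoglobin values of < 5g/dL". Item h covers methaemoglobin of 20% or more, or 10% to below 20% "with associated clinical symptoms of methaemoglobinaemia". Neither item carries a condition on cause or expectedness.

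Section 10.2.1 is a subsection of 10.2. Its title covers laboratory abnormalities as AEs and SAEs, and its examples include haematology. It leaves to the investigator's judgement "deciding whether an abnormal laboratory finding or other abnormal assessment is clinically significant". It then says that clinically significant findings detected during the study, or that "are present at baseline and significantly worsen following the start of the study will be reported as AEs or SAEs". A sentence opening with However follows. It removes from AE and SAE reporting those findings "that are associated with the disease being studied, unless judged by the investigator as more severe than expected" for the subject's condition, as well as findings present at the start that do not worsen.

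Section 10.4 sets a 24-hour limit for all SAEs, running from the point at which the investigator determines that the protocol definition of an SAE is met. In Section 11.3.5.8.2 the haematological AEs are picked out by blinded clinical review of the AE data, and "Haematological AE's will be summarised by preferred term and SOC".

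**The concern.** A fall in haemoglobin is a plausible finding to attribute to acute falciparum malaria. It is also a known concern with the study drug: Section 1.1 reports lower haemoglobin at day 7 with LAPDAP, and the Amendment 2 rationale (Appendix 6) describes haemolysis in a G6PD-deficient patient in a LAPDAP study. A blinded investigator may not be able to separate the two causes in an individual child. A rule that turns on whether a fall is associated with the disease and expected therefore asks for the judgement that item g was written to avoid.

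What is at stake is the prompt report. Haematology is run in local laboratories (Section 6.2.2), and the protocol describes no central laboratory alert. The SAE report is the only 24-hour route it sets out. If a site applies 10.2.1 and never determines that the SAE definition is met, the clock in 10.4 does not start and the event does not enter the AE or SAE tables.

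**Working it through.** The protocol states no figure on this point, so there is none to reproduce. The check sets the rules side by side and then finds which haemoglobin falls each rule reaches.

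**Side by side, for a post-dose haemoglobin value that meets item g**

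| Question | 10.2(g) | 10.2.1 |
|---|---|---|
| Reportable as an SAE? | Yes | No, if associated with malaria and not more severe than expected |
| Depends on presumed cause? | No | Yes |
| Depends on expectedness? | No | Yes, and the term is not defined |
| Refers to the other rule? | No | No exemption for g or h, no order of precedence |

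The 10.2.1 sentence on worsening does not settle the matter, because the disease-associated exclusion comes after it and qualifies it.

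**Which limb of item g applies**

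Inputs: 40% fall and 5 g/dL (Section 10.2(g)); entry haemoglobin of at least 7 g/dL (Section 5.2.1, criterion 6). The baselines below are illustrative assumptions.

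- A fall to 5 g/dL from baseline b is a fraction (b − 5)/b. A 40% fall leaves 0.6 × b. The two limits meet at b = 5/0.6 = 8.33 g/dL.
- b = 7: (7 − 5)/7 = 28.6%. The 5 g/dL limit is crossed first, at any fall greater than 28.6%.
- b = 8: (8 − 5)/8 = 37.5%. The 5 g/dL limit is again crossed first.
- b = 10: 0.6 × 10 = 6.0 g/dL. The 40% limit is reached first.
- b = 12: 0.6 × 12 = 7.2 g/dL. The 40% limit is reached first.

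**Example of the conflict.** A child enters at 7.2 g/dL and falls to 4.8 g/dL. The fall is (7.2 − 4.8)/7.2 = 33.3%, so only the 5 g/dL limb applies. Under 10.2(g) this is an SAE. Under 10.2.1, a site that calls it malaria-related and no worse than expected reports nothing.

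**Reach of the conflict**

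- Transfusion: a treatment, not a laboratory finding, so 10.2.1 does not address it. A transfused child is reportable under item g on that ground alone. The same holds for a child who meets another SAE criterion, such as a new hospitalisation.
- Methaemoglobin: Section 7.11 says chlorproguanil-dapsone induces methaemoglobinaemia, and nothing in the protocol associates it with malaria. The exclusion does not clearly reach item h.
- Falls short of item g: 10 to 6.5 g/dL is (10 − 6.5)/10 = 35%. Without a transfusion or another SAE criterion, only 10.2.1 governs whether this is recorded as an AE. Nothing contradicts it there.
- Laboratory analyses: haematology is scheduled on eight days (0, 1, 2, 3, 7, 14, 28 and 42; Section 6.2.2). It is summarised by arm and time point with counts beyond thresholds (11.3.5.8.3), and by G6PD status (11.3.5.8.4). None of this depends on an AE judgement.

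**The case against.** The strongest reply is that the specific rule governs the general one. Items g and h are numerical, unconditional and written for this study. Section 10.2.1 reads as general text, and its examples include urinalysis, which is not among the laboratory tests in Section 6.2.2. Section 10.4 requires 24-hour reporting of anything meeting the SAE definition, and g and h are part of that definition. The trial also enrols only uncomplicated malaria with haemoglobin of at least 7 g/dL (or haematocrit of at least 25% if haemoglobin is not available), so a value below 5 g/dL is hard to call expected. On this view only a cross-reference is missing.

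Most of this stands. It is the more natural reading, and it is why the point is not serious. It does not remove the point: the protocol states no precedence, expectedness is undefined, and the instruction not to report is explicit and covers SAEs by name.

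A reader might also infer more than the documents support:

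- That the haemoglobin safety comparison as a whole passes through investigator opinion. It does not. Laboratory tests for anaemia and haemolytic anaemia are a safety endpoint of their own (Section 3.2), analysed without AE judgement. Section 11.3.4 adds ongoing blinded safety review and an independent monitoring committee.
- That a loss of power in the SAE tables can be calculated. The protocol gives neither haemoglobin SAE rates nor an under-reporting fraction, and it plans summaries of SAEs, not a test.
- That every lesser fall in haemoglobin or rise in bilirubin must be an AE whatever its attribution. Leaving expected disease manifestations out of AE recording is a defensible policy where the values are captured and analysed.

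**Conclusion.** The inconsistency is real and narrow. For haemoglobin falls of 40% or more and values below 5 g/dL, Sections 10.2(g) and 10.2.1 conflict on a literal reading and must be reconciled. The exposure is to 24-hour SAE reporting and to the completeness of the AE and SAE tables, chiefly for children who meet a haemoglobin limit without transfusion or another SAE criterion. The planned laboratory analyses are unaffected, and blinding limits differential reporting between arms, though it does not recover unreported events.

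How often a site would follow 10.2.1 in place of 10.2(g) cannot be known from the protocol. The conclusion assumes only that some sites could, since the text permits it. Severity: moderate to minor.

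**What to change.** Reconcile the two passages by adding one sentence to Section 10.2.1: events listed under Section 10.2 g and h are always reported as SAEs, regardless of the disease-associated exclusion or the presumed cause, and causality is recorded separately. Naming h as well as g costs nothing and prevents the same question about methaemoglobin. The general exclusion can otherwise stay as written.

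The cost is one sentence in an amendment and a memo to sites. The downside is a few more anaemia SAE reports in both arms, some of which will be due to malaria. No analysis or sample size changes.

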## 10.3. Time Period, and Frequency of Detecting AEs and SAEs

From the time a subject consents to participate in the study until he or she has completed the study (including any follow-up period), all SAEs assessed as related to study participation (e.g., protocol-mandated procedures, invasive tests, or change in existing therapy) or related to a GSK concomitant medication, will be reported promptly to GSK.

## 10.4. Prompt Reporting of SAEs to GSK

SAEs will be reported promptly to GSK as described in the following table once the investigator determines that the event meets the protocol definition of an SAE.

10.4.1.	Timeframes for Submitting SAE Reports to GSK
---------	--

	Initial SAE Reports		Follow-up Information on a Previously Reported SAE	
Type of SAE	Time Frame	Documents	Time Frame	Documents
All SAEs	24 hrs	"SAE" data collection tool	24 hrs	Updated "SAE" data collection tool

## 10.5. AE and SAE Documentation and Follow-up Procedures

The investigator will review and adhere to the following procedures, which are outlined in detail in the AE/SAE section of the SRM:

- Method of Detecting AEs and SAEs
- Recording of AEs and SAEs
- Evaluating of AEs and SAEs
- Completion and Transmission of SAE Reports to GSK
- Follow-up of AEs and SAEs
- Post-study AEs and SAEs
- Regulatory Reporting Requirements for SAEs.

# 11. DATA ANALYSIS AND STATISTICAL CONSIDERATIONS

## 11.1. Hypotheses

The null hypothesis for the primary endpoint is that the parasitological cure rate at Day 28 (PCR corrected) in subjects treated with CDA, is clinically inferior to that for artemether-lumefantrine. The one-sided alternative hypothesis is that the parasitological cure rate for CDA subjects is non-inferior to that of artemether-lumefantrine.

Assessment of these hypotheses will be based on the lower bound of the two-sided 95% confidence interval for the treatment difference (CDA minus artemether-lumefantrine). It will be concluded that CDA is non-inferior if the lower bound is greater than -7%.

## 11.2. Study Design Considerations

#### 11.2.1. Choice of Non-Inferiority Margin

The choice of a 7% non-inferiority margin is difficult to justify in a formal statistical manner as no placebo-controlled studies have ever been conducted for anti-malarial compounds for ethical reasons. Therefore, it is not possible to generate a meaningful indirect confidence interval for CDA – placebo in order to justify the choice of margin in terms of demonstration of efficacy relative to placebo. Consequently, a standard precedent for NI margin in malaria has not been adopted at this time. However, the following reasoning is useful in establishing the relevance of a 7% margin with respect to providing assurance that CDA has a clinically relevant superiority over placebo:

Effective therapies for malaria generally have observed efficacy rates of 90% or above, with the active comparator (Coartem), which is the current gold-standard, achieving at least 95%. Although there are no placebo-controlled data for any anti-malarial compound, the 'untreated' parasitological cure rate for this patient population would be 0% - some immune or semi-immune patients may recover from clinical symptoms but it is highly unlikely that any patients would have complete parasite clearance. Many individuals in malaria-endemic areas harbour malaria parasites but are asymptomatic [Chandler, 2006; Okocha, 2005; Njama-Meya, 2004; Anorlu, 2001].

Therefore, anti-malarial treatments achieve a very large and consistent treatment effect relative to 'no treatment'. Additionally, the primary endpoint under consideration is highly objective. For these reasons, there is a large degree of confidence that if a 7% NI margin is used and CDA demonstrates non-inferiority to Coartem within the constraints of this margin, then CDA would have been shown to be statistically and clinically superior to placebo if a placebo-controlled trial had been performed.

With regard to establishing the clinical relevance of a 7% margin for showing there is no important loss of efficacy if CDA is used to treat this patient population instead of other licenced treatments, several different combination treatments are currently used interchangeably for P. fulciparum malaria. These are considered to achieve at least 90% PCR-corrected parasitological cure at 28-days. However, at the time of protocol development for this study (2005), there were very limited 28-day parasitological cure data available to assess the range of effects observed for the current treatments. Consequently, the assumption that Coartem achieves 95% cure was thought to be relatively conservative and therefore a 5% margin was considered to be too stringent as the true range of effects for the commonly-used anti-malarials could potentially be greater than this. Therefore, 7% was selected to allow some flexibility with respect to the true range of treatment effects across the various anti-malarial combinations.

However, more information regarding 28-day parasitological cure rates for current combination therapies is now available and this has been reviewed in order to re-assess the validity of a 7% NI margin:

